	
a) Length of stay after gastrostomy insertion
 
b) Total variable direct costs by cost category (e.g. medications, suite time, etc.)
 
4) To assess preliminary human factors properties through immediate procedural period data including:
 
a) Overall procedure time
 
b) Physician feedback via surveys on usage properties

Study Design	Single-center, non-randomized, non-blinded feasibility and safety pilot study
Population	The study population will consist of male and female patients (≥ 18 years old) admitted to the hospital and in whom it has been determined by the clinical care team that gastrostomy tube placement is indicated for the administration of nutrition or medications.
Comparator	The comparator group will consist of a matched historical cohort of patients who had gastrostomy tube placement performed using the PRG procedure
Inclusion Criteria	
 • Informed consent must be obtained before any study-specific assessment is performed • Male or female ≥ 18 years of age • BMI ≤ 30, AND BMI ≥ 20 • Indication for gastrostomy tube placement determined to be present by the primary clinical care team • Patient determined to be an appropriate candidate for gastrostomy by the study team • Women of childbearing potential must have negative serum or urine pregnancy test during the current hospitalization

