Exclusion Criteria	
 • BMI > 30, OR BMI < 20 • Temperature \geq 38 C • Systolic BP < 100 or > 180 mmHg • Heart Rate < 50 or > 110 • Presence of a contraindication to being in proximity to a magnet (e.g. pacemaker). • History of prior gastrostomy, gastrectomy (partial or complete), or abdominal trauma or upper-abdominal surgery. • Patients with hematocrit <25%, or a history of blood transfusion within the 14 days prior to screening, or active life-threatening GI bleeding. • Pregnant or nursing (lactating) women, where pregnancy is defined as the state of a female after conception and until the termination of gestation, confirmed by a positive hCG laboratory test. • Involvement in other investigational trials within 30 days prior to screening. • Any other medical condition(s) that may put the patient at risk or influence study results in the investigator's opinion, or that the investigator deems unsuitable for the study. For example, large or collapsed transverse colon overlapping anterior stomach on pre-existing radiographic scan. • Anticipated discharge <36 hrs from gastrostomy
Investigational and Reference Therapy	
Investigational: Placement of gastrostomy tube using the CoapTech device and the PUG technique
 
Reference: A historical cohort of matched patients who underwent PRG placement.

Efficacy Assessments	
Primary efficacy assessment:
 
Describing the feasibility and safety of gastrostomy tube placement using the PUG technique and the CoapTech device.
 
Key preliminary and secondary efficacy assessments
 
 • Description of occurrences of procedure termination 
 ◦ Termination according to protocol ◦ Termination due to other reasons • Description of any reasons for delays in performance of procedure • Determination of overall rate of any adverse events and relatedness-to-device • Description of occurrences of inadvertent puncture of vital organs during performance of procedure • Description of occurrences of infectious complications • Description of occurrences of salvage surgery performed due to complication of procedure • Description of occurrences of requirements for sedation and analgesia during performance of procedure

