The study population will consist of male and female patients (≥ 18 years old) admitted to the participating study site and in whom the primary clinical team has determined that a gastrostomy tube should be placed. The study will focus on patients with a BMI of 20-30 to avoid complications associated with extremes in body habitus.

Inclusion Criteria

Patients eligible for inclusion in this study have to fulfill all of the following criteria:

- Informed consent must be obtained before any study-specific assessment is performed
- Male or female ≥ 18 years of age
- $20 \leq \text{BMI} \leq 30$
- Indication for gastrostomy tube placement determined to be present by the primary clinical care team
- Patient determined to be an appropriate candidate for gastrostomy by the study team
- Women of childbearing potential must have negative serum or urine pregnancy test during the current hospitalization

Exclusion Criteria

Patients fulfilling any of the following criteria are not eligible for inclusion in this study.

- BMI > 30 , or BMI < 20
- Temperature ≥ 38 C
- Systolic BP < 100 or > 180 mmHg
- Heart Rate < 50 or > 110
- Presence of a contraindication to being in proximity to a magnet (e.g. pacemaker).
- History of prior gastrostomy, gastrectomy (partial or complete), or abdominal trauma or upper-abdominal surgery.
- Patients with hematocrit $< 25\%$, or a history of blood transfusion within the 14 days prior to screening, or active life-threatening GI bleeding.
- Pregnant or nursing (lactating) women, where pregnancy is defined as the state of a female after conception and until the termination of gestation, confirmed by a positive hCG laboratory test.
- Involvement in other investigational trials within 30 days prior to screening.
- Any other medical condition(s) that may put the patient at risk or influence study results in the investigator's opinion, or that the investigator deems unsuitable for

the study. For example, large or collapsed transverse colon overlapping anterior stomach on pre-existing radiographic scan.

- Anticipated discharge < 36 hours from gastrostomy.

Method of Assigning Subjects to Treatment Groups

All patients enrolled in the study will have the PUG procedure performed. There is no prospectively enrolled comparator group.

Procedural Team

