After reading the informed consent document, the patient or the patient's legally authorized representative(s) must give consent in writing. Consent must be confirmed at the time of consent by the personally dated signature of the patient, the patient's legally authorized representative(s) and by the personally dated signature of the person conducting the informed consent discussions.

If the patient or the patient's legally authorized representative(s) is unable to read, oral presentation and explanation of the written informed consent form and information to be supplied must take place in the presence of an impartial witness. Consent must be confirmed at the time of consent orally and by the personally dated signature of the patient or by a local legally recognized alternative (eg, the patient's thumbprint or mark) or by the personally dated signature of the patient's legally authorized representative. The witness and the person conducting the informed consent discussions must also sign and personally date the informed consent document. It should also be recorded and dated in the source document that consent was given.

A copy of the signed and dated consent document(s) must be given to the patient or the patient's legal representative(s). The original signed and dated consent document will be retained by the investigator.

The investigator will not undertake any measures specifically required solely for the clinical study until valid consent has been obtained.

Patient Information and Consent: Retrospective Matched Cohort

The study seeks a waiver of consent for recruitment of patients to the comparison matched historical cohort of patients who received the standard of care, PRG, procedure. The involvement in this arm of the research study presents no more than minimal risk of harm to participants and involves no procedures for which written consent is normally required outside of the research context. The same data will be collected in a retrospective fashion using electronic medical record and medical center data sources. Per the study protocol outlined elsewhere, no identifiable patient information will be collected to ensure confidentiality.

Patient Confidentiality

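### The 36-hour anticipated-discharge exclusion applies to PUG subjects but is not stated for the PRG controls, which can bias the comparison of length of stay and stay-driven cost

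*Protocol*

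**What the plan says.** The exclusion list, given in the Protocol Synopsis and again under Population, Exclusion Criteria, ends with "Anticipated discharge <36 hrs from gastrostomy". The same list lets the investigator exclude for any unsuitable medical condition and gives as an example "large or collapsed transverse colon overlapping anterior stomach on pre-existing radiographic scan". In the body, the list is introduced by "Patients fulfilling any of the following criteria are not eligible for inclusion in this study".

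The Synopsis entry for Comparator reads: "The comparator group will consist of a matched historical cohort of patients who had gastrostomy tube placement performed using the PRG procedure". Under Method of Assigning Subjects to Treatment Groups the protocol adds: "There is no prospectively enrolled comparator group". Control data come from records: "The same data will be collected in a retrospective fashion using electronic medical record and medical center data sources" (Patient Information and Consent: Retrospective Matched Cohort).

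Three planned comparisons with these controls matter here, all in the Synopsis under Secondary Objectives:
- objective 3(a), "Length of stay after gastrostomy insertion";
- objective 3(b), variable direct cost by category, within an objective that covers the procedural period and the whole hospital stay;
- objective 1(a), a serious-complication composite that includes puncture of small or large bowel.

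The Synopsis entry for Data Analysis plans ordinary descriptive statistics for the comparison. The SAP says that the study is not powered against standard radiologic placement and sets out no analysis of the controls.

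**The concern.** The 36-hour rule removes patients who are expected to leave soon after the procedure, and time to leaving is the outcome in objective 3(a). If the PRG pool keeps its short-stay patients, the PUG group will look slower to discharge, and costlier wherever cost accrues by the day, for a reason unrelated to the technique.

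Ordinary baseline matching, for example on age, sex or BMI, would not be expected to remove this. The screen is a forward-looking judgement about discharge, which past charts may not record.

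The protocol concedes that the comparison is preliminary and underpowered. That concession is about random error. A selection difference does not shrink with more patients, and the documents do not mention it.

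The colon example raises a related question. If patients with colon over the stomach are kept out of PUG but not out of the control pool, part of any difference in bowel puncture could reflect anatomy.

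**Working it through.** **1. Do the exclusions reach the controls?** Set side by side, the texts leave this open. The list governs inclusion in the study, and the consent section speaks of the retrospective cohort as an arm of the research, so one could argue that it covers them. But the inclusion criteria require informed consent, while a waiver is sought for the controls, so the criteria are written for prospective subjects. No section extends the exclusions to the PRG pool, names a matching variable, ratio or calendar period, or plans an adjustment.

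**2. Length of stay.** The plan states no figure to reproduce. The illustration assumes no true effect of the technique, lognormal stay after insertion with median m and log-SD s, and a 1.5-day screen applied to PUG only. The values of m and s are assumptions.

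- Unscreened mean: m·exp(s²/2).
- With z = ln(m/1.5)/s, the fraction removed by a perfectly predicted screen is 1 − Φ(z).
- Ratio of screened to unscreened mean: Φ(z + s)/Φ(z).

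Worked case, m = 3 and s = 0.8: z = 0.6931/0.8 = 0.866; fraction removed = 1 − 0.807 = 19%; mean = 3·exp(0.32) = 4.13 days; ratio = 0.952/0.807 = 1.18; shift = 4.13 × 0.18 = 0.74 days.

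| Median (days) | Log-SD | Removed | Unscreened mean (days) | Shift in PUG mean (days) | Relative |
|---|---|---|---|---|---|
| 3 | 0.8 | 19% | 4.1 | 0.7 | 18% |
| 3 | 1.2 | 28% | 6.2 | 2.1 | 34% |
| 5 | 0.8 | 7% | 6.9 | 0.4 | 6% |
| 5 | 1.2 | 16% | 10.3 | 1.8 | 17% |
| 10 | 0.8 | 1% | 13.8 | 0.1 | 1% |
| 10 | 1.2 | 6% | 20.5 | 1.2 | 6% |

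The criterion concerns anticipated discharge, so prediction is imperfect. If anticipated stay is actual stay times a lognormal error with log-SD 0.5, the shifts are slightly larger, about 0.3 to 2.2 days. The direction is the same in every row, and the relative size falls as stays lengthen.

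**3. Colon overlap.** Inputs from the SAP: a complication rate of about 4% with radiologic placement, and n = 25. Assumed: prevalence of overlap q = 5% to 20% in unscreened controls, relative risk RR = 2 to 10 for the whole composite, and complete removal from PUG. The screened rate is 0.04/(1 − q + q·RR).

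- q = 0.05, RR = 2: 0.04/1.05 = 3.8%, or 0.95 expected events in 25.
- q = 0.20, RR = 10: 0.04/2.8 = 1.4%, or 0.36 expected events in 25.

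Without screening, 25 × 0.04 = 1.00 event is expected. The shift is therefore 0.05 to 0.64 events.

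**The case against.** The strongest reply is that the asymmetry rests on silence. Matching is undefined, and whoever selects the controls may well apply the chart-checkable exclusions. That stands: the plan can bias the comparison, and one cannot say that it will. But nothing requires the screens, and even a careful chart review could not fully reproduce a judgement about expected discharge.

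Further points also stand:
- The comparison is descriptive and labelled preliminary. The protocol body lists cost and stay under Exploratory Objectives without a PRG contrast. This limits the weight of the point.
- Only cost that accrues with stay is exposed. The 36-hour rule has no evident effect on suite time or direct procedure cost, so a reader who infers that the whole cost comparison is biased goes too far.
- A reader might infer that the shift is 1.5 days whatever the mean. That follows only if stay is exponential, where cutting at 1.5 days always adds 1.5 days. Nothing in the documents supports that shape, and the table shows much smaller values.
- A reader might infer that the puncture composite is tilted in favour of PUG. The documents do not establish this. Colon overlap is an example under investigator discretion, it depends on an existing scan, and nothing says how such patients were handled under PRG. Controls are patients in whom PRG was performed, so attempts abandoned for lack of safe access may already be absent.
- Restricting to patients in hospital at 36 hours conditions on something after the procedure, which the technique could influence through early discharge, complication or death. It therefore suits a sensitivity analysis better than the main comparison.

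**Conclusion.** The point holds for length of stay and stay-driven cost. As written, the plan screens one group on the expected value of the compared outcome and leaves the other group's eligibility unstated. The direction, against PUG, follows if short-stay patients remain in the PRG pool. The size is not derivable from the documents: roughly 0.1 to 2 days on the mean under the assumed lognormal stays, material if stays are short and minor if they are long.

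For the puncture composite the concern is secondary: a plausible but unestablished direction, and less than one expected event in 25 under the assumptions shown. The primary single-arm safety and feasibility outcomes do not use the controls and are unaffected. The change is worth making before control charts are pulled, but it does not threaten the study's main purpose.

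**What to change.** In the SAP:

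1. State that every PUG exclusion that can be checked in a chart is applied to the PRG pool before matching: for example BMI, vital signs, hematocrit, transfusion, prior surgery, and colon overlap where a pre-procedure scan exists. Report how many candidate controls each one removes.
2. For stay and stay-driven cost, add a sensitivity comparison restricted in both groups to patients still in hospital 36 hours after insertion, and show it beside the unrestricted result.
3. State as a limitation that the anticipated-discharge judgement cannot be fully reproduced in past patients. The restriction in item 2 would remove the shift only if anticipated and actual discharge agreed; otherwise part of it remains.

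No PUG enrolment criterion changes. The cost is some SAP wording, slightly more chart screening and fewer eligible controls. The restricted result applies only to patients in hospital at 36 hours.

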Patient Assessments	
 • Physical examination • Vital signs • Height and weight • Calculation of BMI • Abdominal circumference • Laboratory evaluations • Electrocardiogram, if appropriate • Gastrostomy tract depth (measured under ultrasound during procedure)

Other assessments	
 • Preliminary healthcare resource utilization (Costs) 
 ◦ Direct costs of procedure ◦ Environment (e.g. Suite time, etc.) ◦ Laboratory costs ◦ Medication cost ◦ Provider costs ◦ Device costs (estimated) • Length of total ICU and length of total hospital stay after determination made to have gastrostomy tube placed • Indications for gastrostomy placement
Data Analysis	
The primary safety variables are the number and severity of enrolled subjects who have a serious, device-related adverse event during placement of a gastrostomy tube using the PUG procedure.
 
The primary feasibility/efficacy variable is the number of enrolled subjects who have successful placement of a gastrostomy tube using the PUG procedure.
 
Key secondary efficacy variables will be assessed by using common descriptive statistics to a historical cohort of matched subjects who have undergone PRG placement.
 
Data assessments are planned at the end of Phase 1 (n=5), after the 7th subject in Phase 2 (n=12), and at the end of Phase 2 (n≤25).

Introduction

Background

Gastrostomy feeding is an established means of delivering adequate nutrition to patients with an inability to meet their metabolic requirements due to inadequate oral intake. Additionally, the gastrostomy tube can be utilized for medication administration in patients unable to otherwise tolerate oral intake. Traditionally, placement of gastrostomy tubes has been performed endoscopically, radiologically or by either laparoscopic or open surgical techniques. More than 200,000 gastrostomy tubes are placed each year in the United States, and that number is expected to increase as the proportion of the population that is elderly grows (Roche et al 2003, Goldberg et al 2005, Lynch et al 2004).

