- To assess satisfaction of the clinical care team with the performance of the procedure and human factors of the device.

Investigational Plan

Study Design

After assessing eligibility during the screening period, patients who meet the study inclusion and exclusion criteria will be eligible to have gastrostomy tube placement using the PUG technique with the CoapTech device. Proceduralists who have been trained in the performance of the technique will be contacted to arrange a time to have the procedure performed.

Figure 1. Study Design Timeline

Rationale of Study Design

A single arm, prospective, feasibility and safety pilot study was chosen for this first in-human clinical trial of the PUG procedure. If the study were designed to show reduced rates of complications for the PUG procedure compared to PRG then an unachievable number of subjects would be required to be enrolled. A table was generated demonstrating the number of patients required to show that there is a reduction in complications from 3 to 1%. In order to reject a null hypothesis that there is no reduction in complications of the PUG procedure, 1000 subjects would be required to be enrolled with 500 subjects in each arm of the trial. A trial of this size would not be a reasonable first use in human study. The current study will utilize a matched retrospective cohort of patients who had gastrostomy tube placement performed using the PRG procedure for comparison.

The 25-patient study is divided into two phases. The five patients were selected for phase 1 (n=5) as it should allow for sufficient experience with the PUG technique in a controlled environment that will allow for immediate assessment with fluoroscopy or conversion to PRG if needed. With adequate experience from Phase 1, Phase 2 will then allow for some of the PUG procedures to be performed outside of the interventional radiology suite to assess the unique capability of the PUG procedure.

Table 1. Enrollment Required for Prospective Comparison of PUG vs PEG

Total Patients Enrolled (N)	Patients randomized to PUG	Patients randomized to PEG	Expected # of Serious Complications in PUG patients if true rate = 1%		Expected # of Serious Complications in PEG patients if true rate = 3%		P - value for Null hypothesis PUG rate > PEG rate	
			Complications in PUG patients if true rate = 1%	Complications in PEG patients if true rate = 3%	95% CI for PUG rate	95% CI for PEG rate		
8000	4000	4000	40	120	(0.7% - 1.4%)	(2.5% - 3.6%)	<0.0001	

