18. In order to push the gastrostomy tube over the guidewire, cut off the curled end of the guidewire at the shaded section. Discard the curl and balloon catheter. **CAUTION:** cutting outside the shaded region could cause unraveling of the guidewire.
19. Follow standard percutaneous gastrostomy PUSH (Sachs-Vine) technique, with gastrostomy PUSH kit.
20. In situations where coaptive ultrasound has identified a safe gastrostomy tract region, and the PUSH technique is ultimately not feasible or fails, gastrostomy tube placement may be completed using gastropexy. Using a gastropexy kit, place gastropexy anchors followed by standard insertion technique.

Figure 4. Clinical workflow of PUG procedure

Step 2. Coaptation: External magnet (displayed here as rounded white structure) pulls stomach against the abdominal wall by magnetic force.
	

Step 3. Visual confirmation: Balloon is filled with saline and a safe gastrostomy tract location is identified through ultrasound of the stomach and balloon. Moving the external magnet will make minor adjustments to the position of the IBC, to avoid certain anatomy.
	

Step 4. Puncture and coupling: Needle and guidewire are inserted through stomach with ultrasound visualization and coupled with IBC through pigtail mechanism.
	

Step 5+. The final steps of the PUG procedure are consistent with those of the Sacks-Vine technique used in the PEG procedure.
	

Assessments

Efficacy Assessment

The primary safety variables are the number and severity of enrolled subjects who have a serious, device-related adverse event during placement of a gastrostomy tube using the PUG procedure.

The primary feasibility/efficacy variable is the number of enrolled subjects who have successful placement of a gastrostomy tube using the PUG procedure.

Other Assessment – Procedure Failures

In cases where the PUG procedure fails to have successful placement of a gastrostomy tube, reasons for the failure will be determined. These reasons will be divided into those pertaining to the procedure/device itself and those reasons external to the procedure/device.

Other Assessment – Resource Utilization

The costs associated with performance of gastrostomy placement using the PUG technique will be assessed. This includes:

- Direct costs of procedure
- Environment (e.g. Suite time, etc.)
- Laboratory costs
- Medication costs
- Provider costs
- Equipment costs (other than device)

Other Assessment – Clinical Team Survey

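### The PUG-versus-PRG comparison does not say whether each group is counted by attempted or completed procedure, so PUG attempts may be set against completed PRG placements

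*Protocol*

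**What the plan says.** **Controls.** The synopsis (Comparator) describes a "matched historical cohort of patients who had gastrostomy tube placement performed using the PRG procedure". The Reference Therapy entry has "A historical cohort of matched patients who underwent PRG placement". The synopsis Data Analysis entry says key secondary variables will be assessed by "common descriptive statistics to a historical cohort of matched subjects who have undergone PRG placement". The two consent passages on the retrospective cohort (Informed Consent; Patient Information and Consent: Retrospective Matched Cohort) say only that these patients received PRG as standard care. None of these places mentions PRG attempts that were abandoned or failed.

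**PUG subjects.** Under Study Design, "patients who meet the study inclusion and exclusion criteria will be eligible to have gastrostomy tube placement using the PUG technique". Under Method of Assigning Subjects to Treatment Groups, "All patients enrolled in the study will have the PUG procedure performed". Success is not a condition of being in the group.

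**Ways a PUG attempt can end otherwise.** Ten of the 20 numbered procedure steps carry a STOP instruction (1, 2, 3, 6, 7, 9, 10, 11, 13 and 17). The Rationale of Study Design says the Phase 1 setting allows "immediate assessment with fluoroscopy or conversion to PRG if needed". Step 20 lets the tube be completed by gastropexy if the push technique fails.

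**Handling of failures.** Under Other Assessment – Procedure Failures, the protocol says: "In cases where the PUG procedure fails to have successful placement of a gastrostomy tube, reasons for the failure will be determined". The reasons are then sorted into those internal and those external to the device or procedure. The synopsis and the Key Secondary Objectives also ask for a description of terminations.

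**The comparison.** Synopsis Secondary Objectives 1-3 set PUG beside the PRG cohort on complications, cost and length of stay, and call the comparison preliminary and underpowered. The SAP specifies no PRG analysis, and neither document defines an analysis set for one.

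**The concern.** A two-group comparison needs both groups to enter at the same point in the clinical course. Here one group is assembled prospectively before the needle goes in. The other is assembled afterwards from records, apparently on the strength of a tube having been placed by the comparator technique. If so, an abandoned PRG attempt, with its complications, time and cost, is never sampled, while an abandoned PUG attempt is.

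The PUG side has its own gap. The objectives refer to PUG placement without saying whether a subject stopped part-way, converted to PRG or finished by gastropexy belongs in that group. A converted subject carries the exposure, cost and stay of both techniques. A subject finished by gastropexy ends close to the comparator itself, which Secondary Objective 1 identifies as the push-gastropexy form of PRG. Stay measured from tube insertion has no clear start for a stopped subject and an ambiguous one for a converted subject.

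With at most 25 PUG subjects, moving one or two of them into or out of the denominator can change what the table appears to say. Without a rule, that choice would be made after the data are known.

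**Working it through.** **1. The plan's own figures.** With no events in 25 subjects, the two-sided 95% exact upper bound is 1 − 0.025^(1/25) = 0.137. This agrees with the SAP's 13.7%. The bound belongs to the single-arm safety question and does not depend on how conversions are counted. The SAP also gives about 4% as the complication rate of radiologic placement, which is used as a reference below. The documents give no PUG conversion rate, no PRG failure rate and no complication rate in failed attempts. These are assumptions from here on.

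**2. Entry points side by side.**

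| | PUG group | PRG controls |
|---|---|---|
| Identified | Before the attempt, at eligibility | Afterwards, from records |
| Success needed to be counted? | Not for the primary variables; unstated for the comparison | Suggested by the Comparator wording; left open by the consent sections |
| Stopped or failed attempts | Reasons described; place in the comparison unstated | Not mentioned |
| Finished by another technique | Possible (PRG, gastropexy); counting unstated | Not mentioned |

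**3. What the PUG denominator does.** Let k of 25 subjects convert (assumed k = 1 to 5), with one complication in total.

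| k | Completed placements, 25 − k | Event in a converted subject: by attempt / by completion | Event in a completed subject: by attempt / by completion |
|---|---|---|---|
| 1 | 24 | 1/25 = 4.0% / 0/24 = 0% | 1/25 = 4.0% / 1/24 = 4.2% |
| 3 | 22 | 1/25 = 4.0% / 0/22 = 0% | 1/25 = 4.0% / 1/22 = 4.5% |
| 5 | 20 | 1/25 = 4.0% / 0/20 = 0% | 1/25 = 4.0% / 1/20 = 5.0% |

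The choice can move the rate either way, depending on who has the event.

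**4. Attempts against completions when the techniques are truly equal.** Let p = 4% be the complication rate in completed placements, f the share of attempts not completed, and q the complication rate in those attempts. The rate by attempt is (1 − f)p + fq, and the control rate by completed placement stays at 4.0%.

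- f = 5%, q = 10%: 0.95 × 0.04 + 0.05 × 0.10 = 4.3%
- f = 20%, q = 30%: 0.80 × 0.04 + 0.20 × 0.30 = 9.2%
- f = 20%, q = 4%: 0.80 × 0.04 + 0.20 × 0.04 = 4.0%
- f = 20%, q = 0%: 0.80 × 0.04 + 0.20 × 0 = 3.2%

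The spurious difference is positive, nil or negative according to whether q is above, equal to or below p. Seven of the ten STOP steps (1, 2, 3, 6, 7, 9, 10) precede the needle puncture at Step 11, and three (11, 13, 17) come at or after it. A low q is therefore as plausible as a high one.

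**5. Cost.** If each conversion adds one PRG procedure cost c, and other costs are the same in converted and completed subjects, counting by attempt raises mean PUG cost by (k/25)c. That is 0.04c for k = 1 and 0.20c for k = 5.

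**6. Will the case arise?** If each of 25 attempts independently fails to complete with probability f, the chance of at least one is 1 − (1 − f)^25: 72% at f = 5%, 93% at 10% and 99.6% at 20%.

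**The case against.** The strongest reply is that the asymmetry is not stated in so many words. The consent sections speak of receiving the PRG procedure, which can include an unsuccessful attempt. The protocol also uses the word placement for the process elsewhere, adding the word successful when it means the outcome. This stands: a reader might infer that controls are restricted to completed PRG placements, but the documents do not settle it. The Comparator wording points that way, and nothing directs anyone to look for failed attempts.

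A reader might also infer that converted subjects will be dropped. The text does not support that. All enrolled patients have PUG performed, the primary variables count enrolled subjects, and no exclusion of failures is written anywhere. What is missing is a rule for the comparison.

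Much of the data needed is already planned. Terminations are described, every medical or surgical procedure is recorded with its date, time and reason (Concomitant Medications, Therapies, and Interventions), and Table 3 records event onset and relatedness. The synopsis (Other assessments) and the Exploratory Objectives already measure stay from the decision to place a tube. This stands and makes the repair cheap, but collecting the data does not say who is counted.

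Finally, the effect may be small. Conversion to PRG is named only for Phase 1 (five subjects). The only success rate in the Background is 95-100% for PEG. If PRG were similar (an assumption), 0 to 5% of control attempts would be missed, or 0 to 1.25 per 25. The comparison is secondary, descriptive and openly underpowered. That limits the weight of the point. It does not excuse mismatched denominators, because low power concerns precision and this concerns what is being compared.

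**Conclusion.** The point holds as a defect in the definition of a secondary comparison. For Secondary Objectives 1-3, the entry points of the two groups are not aligned, and the place of stopped, converted or gastropexy-completed PUG subjects is not stated. Read most naturally, the text compares PUG attempts with completed PRG placements.

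The size is not determinable from the documents. Under assumed conversion counts of 1 to 5, the completed-placement denominator runs from 24 to 20. One event in a converted subject is then 4% or 0% depending on the convention, against an SAP reference rate of about 4%.

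It is tempting to say that counting by attempt favours PRG and that dropping conversions favours PUG. For complications the documents do not support either, since most STOP steps come before any puncture. For cost, dropping conversions would lower the PUG mean only under the assumptions in step 5 of the working.

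The primary safety and feasibility variables and the SAP's sample-size reasoning count enrolled subjects and are not affected. The change should be made, but the trial's main conclusions do not depend on it.

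**What to change.** Amend the wording of Comparator, Reference Therapy and Secondary Objectives 1-3, and carry it into the SAP:

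- Define both cohorts by attempted procedure.
- Select as controls all matched patients in whom PRG was started, including aborted or failed attempts as far as hospital records identify them. Say so if the records cannot.
- Analyse every subject in whom PUG was started in the PUG group, whatever the final technique. Report the number of stopped attempts, conversions and gastropexy completions, and whether each event came before or after conversion. The planned procedure and adverse event records supply this.
- Measure stay in both groups from the decision to place a tube, as the plan already does elsewhere.
- Show completed placements only as a secondary table.

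This changes analysis definitions only; no clinical step is altered. The cost is a few sentences and slightly more chart work to find aborted PRG attempts. PUG cost and stay may also look less favourable once conversions are included.
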